9. FUNDING

Funding for the present trial is provided by NHTSA in partnership with EMF. The funding agencies have no role in the design and conduct of the study, collection, management, analysis, and interpretation of the data, preparation, review, or approval of the manuscript, or the decision to submit the manuscript for publication.

10. PUBLICATIONS

We plan to write 3 separate main manuscripts describing findings related to Cogorts 1,2, &3. The manuscripts will adhere to the CONSORT guidelines. The principal investigator will be responsible for assigning authorship position and will follow authorship guidelines from the International Committee of Medical Journal Editors. At a minimum, all members of the Investigator Team will be included in the primary author list. The main results will be presented at an international conference. The trial results will be shared with participating sites and via press releases but not directly with the participants.

11. DATA SHARING

Six months after the publication of the last results, all de-identified individual participant data will be made available for data sharing. Procedures, including re-coding of key variables, will be put in place to allow for complete de-identification of the data. All relevant trial-related documents, including the protocol, data dictionary, and the main statistical code, will be shared along with the data. There will be no predetermined end date for the data sharing. Data will be available for any research purpose to all interested parties who have approval from an independent ethics review committee and who have a methodological sound proposal as determined by the steering committee of the current trial. Interested parties will be able to request the data by contacting the principal investigator. Authorship of publications emerging from the shared data will follow standard authorship guidelines from the International Committee of Medical Journal Editors and might or might not include authors from the steering committee depending on the nature of their involvement.

12. INTELLECTUAL PROPERTY

We will submit a disclosure of intellectual proprerty to the University of Pittsburgh between primary analyses and publication submission. Inventors to be listed include [name], [name] and [name].

13. TASKS AND RESPONSIBILITIES

Principal investigator: Overall responsibility for protocol development, intervention development, budget overview, data dictionary development, ethical approval, trial registration, daily management, trial oversight and collection of adverse events, and the data and safety monitoring board, assessment of overall recruitments, potential recruitment of additional sites, data analysis, and dissemination and presentation of results.

Co-Investigators: Site-specific enrollment, education of personnel at participating sites, reporting of site-specific issues or challenges to the principal investigator, participant consent for data collection, collecting and reporting data regarding adverse events. Also protocol development, data dictionary development, trial oversight, dissemination of results.

Steering committee: Protocol development, data dictionary development, trial oversight, dissemination of results.

Appendix: Screening Questions

Question	How old are you?	18 years old	19 years old	20 years old	21 years old
Code	age	0	1	2	3
Question	What is your sex?	Female	Male		
Code	sex	0	1		
Question	Are you Hispanic or Latino?	No	Yes		
Code	hisp	0	1		
Question	What is your race? (Select one or more responses.)	Black or African American	White	Asian	Other
Code	brace, wrace, asian, rother	0/1	0/1	0/1	0/1
Question	Are you currently enrolled in school?	No	Yes, High School	Yes, College	
Code	school	0	1	2	
	The following questions ask you to recall times you have been in a car over the past 2 weeks.				
Question	How often have you driven a car?	Never	A few times	Most	Every
Code	driver	0	1	days 2	day 3
Question	How often did you wear a seat belt when you drove a car?	Never	A few times	Most of the time	Always
Code	drive_seatbelt	0	1	2	3
Question	How often have you been a passenger in the front seat of a car?	Never	A few times	Most days	Every day
Code	pass_front	0	1	2	3
Question	How often did you wear a seat belt when you were a passenger in the front seat ?	Never	A few times	Most of the time	Always
Code	pass_seatbelt1	0	1	2	3
	How often have you been a passenger in the back seat of a car?	Never	A few times	Most days	Every day
	pass_back	0	1	2	3
	How often did you wear a seat belt when you were a passenger in the back seat?	Never	A few times	Most of the time	Always
	pass_seatbelt2	0	1	2	3
Question	How often did you type on your phone while you were driving and when the car was moving?	Never	A few times	Most of the time	Always
Code	distract	0	1	2	3
Question	Have you driven a vehicle within 3 hours after consuming 3 or more alcoholic drinks?	No	Yes		
Code	drinks	0	1		
	Thanks! Please hand the iPAD back to the Researcher.				

RA enters code: SAVE

Program displays which risks+

Script RA tells pt they are potentially eligible for study or thanks them for their time.

If eligible pt interested, RA asks the following:

Question	Do you have a personal cell phone with text messaging ?	No	Yes
Code	sms	0	1
Question	Do you plan to drive and/or ride in a vehicle in the next month?	No	Yes
Code	future	0	1
Question	Do you plan to change phone numbers in the next 3 months?	No	Yes
Code	phone	0	1

Logic If sms=0 or future=0 or phone=1, they are excluded.

RA either thanks them for their time or starts informed consent.

RA goes to WebDataXpress site

Appendix: Baseline Questions

Quest ion Who do you live with?	l live alone	Friend(s), same sex	Friend(s), other sex	Parents or family		
Code livew	0	1	2	3		
Quest ion	No	Yes, part- time	Yes, full time			
Code emply	0	1	2			
Quest ion	Uncomfortab le	Forgot	Don't think they help	Like freedo m	Other	l always wear my seat belt
Code seatbelt_reasons	0	1	2	3	4	5
Quest ion If other, state reasons						
Code seatbelt_other						
Quest ion	Never	Rarely	Most of the time	Always		
Code	0	1	2	3		
Quest ion How dangerous is it to not wear a seat belt?	Not at all	Somewhat	Very	Comple tely		
Code danger_seatbelt	0	1	2	3		
Quest How much do you agree: I have complete control over whether I wear a ion seat belt.	Strongly Disagree	Disagree	Somew hat Agree	Mostly agree	Strongly Agree	
Code control_sb	0	1	2	3	4	
Quest Check off all the reasons you have typed on your phone while driving? ion	l could not wait	I don't think it affects my driving	It was an emerge ncy	lt is fun	l get bored driving	l do not use my phone while driving
Code twd_reasons	0	1	2	3	4	5
Quest ion How often do your friends type on their phones while driving?	Never	Rarely	Most of the time	Always		
Code	0	1	2	3		
Quest ion How dangerous is it to type on your phone while driving?	Not at all	Somewhat	Very	Comple tely		
Code danger_twd	0	1	2	3		
Quest How much do you agree: I have complete control over whether I type on ion my phone while driving.	Strongly Disagree	Disagree	Somew hat Agree	Mostly agree	Strongly Agree	
Code control_twd	0	1	2	3	4	
Quest Check off all the reasons you have driven a car after drinking alcohol? ion	l had no other opiton	I don't think it affects my driving		l am careful	It is fun	l do not drive after dirnking alcohol
Code dd_reasons	0	1	2	3	4	5
Quest ion How often do your friends drive after drinking alcohol?	Never	Rarely	Most of the time	Always		
Code friends_dd	0	1	2	3		
Quest How dangerous is it to drive soon after drinking more 3 or more alcoholic ion drinks?	Not at all	Somewhat	Very	Comple tely		
Code danger_dd	0	1	2	3		

Quest How much do you agree: I have complete control over whether I type on ion my phone while driving.	Strongly Disagree	Disagree	Somew hat Agree	Mostly agree	Strongly Agree
Code control_dd	0	1	2	3	4

Quest Answer the following questions about yourself.	Strongly Disagree	Disagree	Somew hat Agree	Mostly agree	Strongly Agree	
cat code	0	1	2	3	4	
Questi When I feel bad, I will often do things I later regret in order to make myself on feel better now.						
Questi Sometimes when I feel bad, I can't seem to stop what I am doing even on though it is making me feel worse.						
Questi on When I am upset I often act without thinking.						
Questi on When I feel rejected, I will often say things that I later regret.						
On l generally like to see things through to the end.						
Questi on Unfinished tasks really bother me.						
Once I get going on something I hate to stop.						
on Questi I finish what I start.						
Questi on My thinking is usually careful and purposeful.						
On on I like to stop and think things over before I do them.						
$\underset{on}{^{Questi}}$ I tend to value and follow a rational, "sensible" approach to things.						
on Questi I usually think carefully before doing anything.						
Questi on I quite enjoy taking risks.						
Questi I welcome new and exciting experiences and sensations, even if they are on a little frightening and unconventional.						
on Questi I would like to learn to fly an airplane.						
Questi I would enjoy the sensation of skiing very fast down a high mountain on slope.						
Questi When I am in great mood, I tend to get into situations that could cause me on problems.						
Questi on I tend to lose control when I am in a great mood.						
Questi Others are shocked or worried about the things I do when I am feeling on very excited.						
Questi on I tend to act without thinking when I am really excited.						
Questi on How long have you been driving a car?	Less than 6 months	6 months to 1 year	1-2 years	2-5 years	More than 5 years	never driven
Code long_dr Questi How many times in the last 12 months have you received a traffic ticket? on (Not including parking tickets)	0	1	2	3	4	5
Code tix	#					
Questi on As a driver of a car, have you been in a crash in the past 12 months?						
Code crash	#					
Questi How many days over the last month have you drank more than (3 drinks on for women/ 4 drinks for men)?						

Code Imbinge

#

Questi How many days over the last month have you used cannabis (marijuana, on pot, has, grass, etc)?

Code Imbinge

#

Thanks, This ends your baseline survey. Please hand me back to the Researcher.

Day & Time Incoming Outgoing Enrollment Hi [_NAME_]. Welcome to to the SaVE Study For the next 2 weeks, each Sunday, we will ask you about your seat belt use in the past week If you complete at least 50% of the text queries, you will be eligible for the rest of the study Any If at any time you wish to stop receiving texts, just text us "stop" response Sunday, 4pm Hi [_NAME_], it's theSaVE Team checking in How often have you been a passenger or driver in a car the past week? 0=never; 1=a few times; 2=most days; 3=every day [Missing] We missed your response. Text us how often you have been a passenger or driver in a car the past 2 hours x1 week [Missing] 2 hours х2 You must be busy. We will check in next week [Nonsense We don't understand. Please text us a response option: 0=never; 1=a few times; 2=most days; 3=every 1 day 0 ΟK 1,2,3 How often did you wear a seat belt? 0=never; 1=a few times; 2=most of the time; 3=every time [Missing] 1 hour x1 We missed your response. Text us how often you wore a seatbelt [Missing] 1 hour You must be busy. We will check in next week x2 We don't understand. Please text us a response option: 0=never; 1=a few times; 2=most of the time; [Nonsense 3=every time 1 0,1,2,3 Thanks Day 15 Due to your low response rate, you will be withdrawn from the SaVE Study (Monday) For further information about seat belt safety, go to www.NHTSA.gov

Appendix: SMS Run-In: Seat belt

Appendix: SMS Run-In: Typing While Driving (TWD)

Day & Time	Incomin g	Outgoing
Enrollment		Hi [_NAME_]. Welcome to to the SaVE Study
		For the next 2 weeks, each Sunday, we will ask you about your seatbelt use in the past week
		If you complete at least 50% of the text queries, you will be eligible for the rest of the study
	Any	
	respons e	If at any time you wish to stop receiving texts, just text us "stop"
Sunday,		
4pm		Hi [_NAME_], it's theSaVE Team checking in
		How often have you driven a car the past week? 0=never; 1=a few times; 2=most days; 3=every day
	[Missing	We missed your response. Text us how often you have been a passenger or driver in a car
2 hours] x1	the past week?
0 haven	[Missing	Veu must be busy. We will check in most week
2 hours] x2 [Nonsen	You must be busy. We will check in next week We don't understand. Please text us a response option: 0=never; 1=a few times; 2=most
	se]	days; 3=every day
	0	OK.

	1,2,3 [Missing	When driving, how often did you type on your phone when the car was moving? 0=never; 1=a few times; 2=most of the time; 3=every time We missed your response. Text us how often you typed on your phone when the car was				
1 hour] x1 [Missing	moving				
1 hour] x2 [Nonsen se]	You must be busy. We will check in next week We don't understand. Please text us a response option: 0=never; 1=a few times; 2=most of the time; 3=every time				
	0,1,2,3	Thanks				
Day 15 (Monday)		Due to your low response rate, you will be withdrawn from the SaVE Study				
	For further information about safe vehicle use, go to www.NHTSA.gov					

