2.9 SMS Onboarding

We will then ask participants to text in a keyword to our program phone number. Only phone numbers that match the phone numbers entered by the RA in the enrollment process wil receive texts. Once this match is recognized, participants will receive several texts welcoming them to the study and describing the 2-week run-in. Each chohort will receive similar yet unique welcome messages tailored to their risk behavior.

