2.10 SMS Run-in

All participants will complete a 2-week run-in period where they complete weekly SMS assessments related to their target risk behavior without receiving any feedback or goal support. The primary purpose of the run-in is to exclude noncompliant subjects. Only participants who respond to at least 50% of the SMS queries in week 1 & 2 will be eligible to continue in the study. The secondary purpose is to identify the post-enrollment/ pre-intervention vehicle risk behaviors that may occur as a result of assessment reactivity. We expect that simply the act of enrolling in a study about vehicle risk and completing weekly SMS assessments of risk may result in reduced risk behaviors.

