Appendix: SMS Run-In: Drink Driving

Day & Time	Incoming	Outgoing
Enrollment		Hi [_NAME_]. Welcome to to the SaVE Study For the next 2 weeks, each Sunday, we will ask you about your seatbelt use in the past week If you complete at least 50% of the text queries, you will be eligible for the rest of the study
	Any response	If at any time you wish to stop receiving texts, just text us "stop"
	•	
Sunday, 4pm		Hi [_NAME_], it's theSaVE Team checking in How often have you driven a car the past week? 0=never; 1=a few times; 2=most days; 3=every day
2 hours	[Missing] x1 [Missing]	We missed your response. Text us how often you have been a passenger or driver in a car the past week?
2 hours	x2 [Nonsense]	You must be busy. We will check in next week We don't understand. Please text us a response option: 0=never; 1=a few times; 2=most days; 3=every day
	0 1,2,3 [Missing]	OK Have you driven a vehicle within 3 hours after consuming 3 or more alcoholic drinks?
1 hour	x1 [Missing]	We missed your response. Text us Yes or No.
1 hour	x2 [Nonsense	You must be busy. We will check in next week
]	We don't understand. Please text us either Yes or No
	No	Thanks
Day 15		
Day 15 (Monday)		Due to your low response rate, you will be withdrawn from the SaVE Study
,		For further information about safe vehcile use, go to www.NHTSA.gov

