	How often have you driven a car the past week? 0=never; 1=a few times; 2=most days; 3=every day
[Missing] x1	We missed your response. Text us how often you driven a car the past week?
[Missing] x2	You must be busy. We will check in tomorrow
[Nonsense]	We don't understand. Please text us a response option: 0=never; 1=a few times; 2=most days; 3=every day
0	ОК
1,2,3	Have you driven a vehicle within 3 hours after consuming 3 or more alcoholic drinks?
[Missing] x1	We missed your response. Text us whether you have driven within 3 hours of drinking 3 or more alcoholic beverages.
[Missing] x2	You must be busy. We will check in next week
[Nonsense]	We don't understand. Please text us Yes or No.
No	[Posiitve Reinforcement Message]
Yes	[Social Norms Message]
Goal met	[Goal Met Message]
Goal not met	[Goal Not Met Message]
	Would you be willing to commit to a goal to not drive after drinking this week?
[Missing] x1	We missed your response. Text us whether you'd be willing to set a goal?
[Missing] x2	You must be busy. We will check in next week
[Nonsense]	We don't understand. Please text us either yes or no
No	[No Goal Roll Library Message]
Yes	[Goal Reinforcement Message]

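### The Cohort 2 and 3 run-in texts announce seat-belt questions, and their reminders do not repeat the driving question that decides who is asked about the risk (wrong as written, minor)

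*Combined protocol and SAP*

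**What the plan says.** Section 2.9 (SMS Onboarding) says that each cohort receives "similar yet unique welcome messages tailored to their risk behavior". Section 2.10 (SMS Run-in) says that in the run-in "they complete weekly SMS assessments related to their target risk behavior without receiving any feedback or goal support", and gives as its secondary purpose the measurement of behavior after enrollment and before intervention, when reactivity to assessment may already be at work.

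The appendix scripts for the typing run-in and the drink-driving run-in both open with the same announcement for the two weeks: "we will ask you about your seatbelt use in the past week". The Sunday risk items that follow are the right ones: "When driving, how often did you type on your phone when the car was moving" for Cohort 2 and "Have you driven a vehicle within 3 hours after consuming 3 or more alcoholic drinks" for Cohort 3.

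Before the risk item there is a filter question on car use in the past week. A reply of 0 ends the session; 1, 2 or 3 opens the risk item. In Cohorts 2 and 3 the first version of this question concerns driving only. After two hours without a reply, the run-in reminder says "Text us how often you have been a passenger or driver in a car the past week". The Cohort 2 intervention reminder is also about riding or driving. The Cohort 3 intervention reminder is not: "Text us how often you driven a car the past week".

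Section 2.13 says that controls go on receiving weekly assessments for 12 more weeks. The appendix prints no separate control script.

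**The concern.** These are outgoing messages and branching rules, not background text. Section 2.12 says that queries and branching logic are written before enrollment and points to the appendix for the intervention material. If the scripts are programmed as printed, two things follow.

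First, participants in two of the three trials are told that they will be monitored on a behavior other than their target. Reactivity is what the run-in is meant to capture, and the run-in is one segment of the slope analysis in section 3.1.4.

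Second, the filter question changes with the timing of the reply, and in Cohort 3 also with the study period. Weekly SMS reports feed the GEE slopes and replace missing week-8 and week-14 survey answers (section 4.2.3), so a wording difference has a route into the analyzed data.

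**Working it through.** No published figure depends on this point, so the check is a comparison of the scripts.

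| Script | Topic announced | First filter question | Reminder | Risk item |
|---|---|---|---|---|
| Run-in, Cohort 1 | Seat belts | Riding or driving | Riding or driving | Seat belts |
| Run-in, Cohort 2 | Seat belts (wrong) | Driving | Riding or driving (differs) | Typing |
| Run-in, Cohort 3 | Seat belts (wrong) | Driving | Riding or driving (differs) | Drink driving |
| Intervention, Cohort 1 | Seat belts | Riding or driving | Riding or driving | Seat belts |
| Intervention, Cohort 2 | Driving safety | Driving | Riding or driving (differs) | Typing |
| Intervention, Cohort 3 | Driving safety | Driving | Driving | Drink driving |

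The Cohort 3 intervention script is identified here by its drink-driving item, because its heading is printed after the table. Cohort 1 is consistent throughout. The errors in the other rows look like text carried over from it.

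**Reach of the welcome error.** Sections 2.1 and 4.1 plan 100 + 100 = 200 participants in Cohorts 2 and 3. Everyone onboarded gets the text. Randomization follows the run-in (sections 2.10 and 2.11), so both future arms get it alike.

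**Who is affected by the reminder.** Take a participant who rode in a car that week but did not drive.

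- Replying to the first question: answers 0 and the session ends, in every Cohort 2 and 3 script.
- Replying to the Cohort 3 run-in reminder: answers 1 to 3, is asked about drink driving, and truthfully says no.
- Replying to the Cohort 3 intervention reminder: answers 0 and the risk item is skipped.

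The true state is no risk in all three cases. The record differs only as an explicit no versus a skipped item. The plan does not say how a skipped item is coded. If it counts as missing, section 4.2.3 fills it with the worst adjacent SMS week, which could assign a risk to someone who did not drive.

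**When an arm difference is possible.** Run-in is weeks 1 to 2, intervention weeks 3 to 8, and follow-up weeks 9 to 14 (2 + 6 + 6 = 14). Section 2.12 describes the intervention arm's last six weeks as assessment only, as section 2.13 does for controls. Even if controls keep the run-in script, the contrast is therefore confined to about weeks 3 to 8, and to Cohort 3, since the Cohort 2 reminder is the same in both scripts.

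**How far it could reach the week-8 outcome.** That outcome comes from the web survey (section 2.14); SMS enters only where the survey is missing. The plan gives attrition for Cohort 1 alone: 300 × 0.9 × 0.8 = 216. Assuming the same rates in Cohort 3, 100 × 0.9 = 90 are randomized and 90 × (1 − 0.8) = 18 lack the survey, about 9 per arm. Only those among them who replied late and rode without driving in a relevant week are affected. That share is not given, so the number lies anywhere from 0 to about 18. The GEE slopes use all weekly reports and are not bounded in this way.

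**The case against.** The best defense is that this is a copying slip in one enrollment message. Participants have by then been screened on all three behaviors and have completed an identical baseline survey that asks about each of them, and every Sunday risk item names the right target. Cohorts 2 and 3 are exploratory (section 2.1), the outcome is a web survey, and the powered Cohort 1 scripts are correct. All of this stands, and it sets the severity. It does not remove the contradiction with section 2.9 or the mismatch between question and reminder.

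A reader might go further and infer that the weekly data are filtered differently by arm. The documents do not say so: the printed contrast is run-in against intervention. Section 2.13 suggests that controls stay on the run-in wording but does not state it. Nor is there support for carrying such a difference through to week 14, since both arms are described as assessment only by then.

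A reader might also infer that announcing seat belts spoils the baseline or biases the treatment comparison. One mistaken text, sent alike to everyone before randomization, does not support that. At most it clouds a descriptive reading of reactivity.

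**Conclusion.** Wrong as written, minor severity. Two findings need no assumption: the welcome texts for up to 200 planned participants name the wrong topic, and in both cohorts' run-ins, and in the Cohort 2 intervention, the reminder asks a different filter question from the one it follows up. A third is also on the page: the Cohort 3 reminder changes between run-in and intervention, two periods whose slopes the plan intends to examine.

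An arm difference in Cohort 3 in about weeks 3 to 8 is conditional on controls keeping the run-in script. Its effect on recorded risk is further conditional on a skipped item being treated differently from an explicit no. Its size cannot be computed and is probably small. It reaches outcomes only through imputation of missing surveys and the GEE slopes, in exploratory cohorts. The Cohort 1 sample size and primary analysis are untouched.

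**What to change.** - In the Cohort 2 and Cohort 3 run-in welcome texts, replace seat-belt use with typing while driving and drink driving respectively.
- Make each Cohort 2 and 3 reminder repeat its own first question, on how often the participant drove.
- Print the control script for weeks 3 to 14 and the assessment-only script for weeks 9 to 14 of the intervention arm, and use identical assessment wording in run-in, intervention and control.
- State in section 4.2.3 that in Cohorts 2 and 3 a reply of 0 to the driving question is coded as no risk that week, not as missing.
- In the typing and drink-driving intervention scripts, some non-response messages promise contact the next day although the assessment is weekly. Align them with the seat-belt script, which refers to the following week.

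The cost is a few text edits before programming and one added coding rule. Sample size, schedule and the main analysis do not change. If anyone has already been onboarded, record the date of the change so that run-in data before and after it can be told apart.
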